3.4 Other Safety Endpoints

Non-ocular AEs, laboratory profiles, physical examinations, and vital signs will be assessed throughout the study.

3.5 Pharmacokinetic Endpoints

No pharmacokinetic endpoints

3.6 Histopathologic/Biomarker Tissue Evaluation Endpoints

During this study, tumor biomarker samples will be collected. Optional tissue collection may include tumor tissue samples from the subjects' initial surgery, repeated resection(s) and/or post-mortem corneal tissue samples. Tumor samples may be analyzed for genetic factors contributing to the subject's response to depatuxizumab mafodotin, or other study treatment, in terms of tolerability and safety. Such genetic factors may include genes for drug metabolizing enzymes, drug transport proteins, genes within the target pathway, or other genes believed to be related to drug response. Some genes currently insufficiently characterized or unknown may be understood to be important at the time of analysis. The samples may be analyzed as part of a multi-study assessment of genetic factors involved in the response to depatuxizumab mafodotin or drugs of this class. The samples may also be used for the development of diagnostic tests related to depatuxizumab mafodotin (or drugs of this class). Corneal tissue will be assessed to further characterize histopathologic features of OSEs. The samples may be retained for no longer than 20 years after study completion or per local requirements.

Exploratory Endpoints of this study are:

Effectiveness of the prophylactic regimen with regard to symptom severity as assessed by:

1. Individual items on the CEAE scale – degree of photophobia at each visit; impact of ocular discomfort on visual Activities of Daily Living (vADLs) at each visit; reading score (impact on blurred vision) at each visit.
2. Visual Quality of Life (vQOL) score changes

Effectiveness of the intervention with regard to symptom severity as assessed by:

1. Individual items on the CEAE scale – degree of photophobia at each visit; impact of ocular discomfort on vADLs at each visit; reading score (impact on blurred vision) at each visit.
2. vQOL score changes
3. % of subjects with improvement on vQOL

Overall survival (OS)

Progression free survival (PFS)

4 INVESTIGATIONAL PLAN

4.1 Overall Study Design and Plan

A schematic of the study design is shown in [Figure 1](#). Further details regarding study procedures are located in the Operations Manual, Section 3. See [Section 5.1](#) for information regarding eligibility criteria.

This is a Phase 3b open-label, randomized, exploratory study to evaluate the effect of 3 ophthalmologic prophylactic treatment strategies for the management of OSEs in subjects with newly diagnosed, EGFR-amplified GBM who are being treated with depatuxizumab mafodotin in addition to standard frontline treatment with chemoradiation (RT/TMZ) followed by adjuvant TMZ. Approximately 90 subjects will be enrolled at approximately 30 research sites.

During the Chemoradiation Phase, all subjects will undergo focal RT, with one treatment of ~2 Gy given daily 5 days per week over approximately 6 weeks (and no more than 7 weeks), for a total of ~60 Gy. TMZ will be administered 75 mg/m² orally once daily continuously from Day 1 of radiotherapy to the last day of radiation for a maximum of 49 days. All subjects will receive depatuxizumab mafodotin at 2.0 mg/kg IV infusion once every 2 weeks (on Day 1 of Weeks 1, 3, and 5) during this period.

Treatment in the Chemoradiation Phase must begin ≤ 49 days after surgery diagnosing GBM. Occasionally, a subject might require a staged or two-surgery approach; for such cases, subjects will still be considered eligible for this study if the latest surgery was performed within 30 days after the initial surgery/biopsy diagnosing GBM and if all screening procedures are completed and chemoradiation treatment begins ≤ 49 days after the last surgery.

The start of the first cycle during the Adjuvant Phase will be scheduled approximately 28 days after the last day of chemoradiation. The AbbVie Therapeutic Area Medical Director should be notified if Adjuvant Phase treatment is to be started more than 42 days after the last day of chemoradiation.

During the Adjuvant Phase, all subjects will receive oral TMZ (150 – 200 mg/m²) once daily, on Days 1 – 5 of each 28-day cycle, for 6 – 12 cycles, depending on local standard of care. All subjects will receive depatuxizumab mafodotin at 1.25 mg/kg IV infusion once every 2 weeks (on Day 1 and Day 15 of each 28-day cycle) for 12 cycles. Adjuvant treatment will be discontinued upon determination of tumor progression as defined by Response Assessment in Neuro-Oncology Working Group (RANO) criteria (Operations Manual, Appendix I), unacceptable toxicity, or refusal to continue study treatment.

Subjects will be randomized to 1 of 3 prophylactic eye treatment arms (1:1:1), to be administered with each infusion of depatuxizumab mafodotin (during both Chemoradiation Phase and Adjuvant Phase):

- Arm A (SS) – Standard Steroids
- Arm B (SS/VC) – Standard Steroids + Vasoconstrictor + Cold Compress
- Arm C (ES/VC) – Enhanced Steroids + Vasoconstrictor + Cold Compress

Subjects will be monitored at regular intervals for OSEs by AE reports and by ophthalmology examinations (including slit lamp examination and visual acuity testing).

[figure not shown]
For subjects who demonstrate inadequate control of OSEs with the initial prophylactic strategy, according to predefined criteria for loss of visual acuity and/or OSE symptom severity, intervention with a BCL will first be employed (Figure 2). Subjects who continue to demonstrate inadequate response to BCL intervention (CEAE Grade 3 or higher OSE symptom severity) will be eligible for unrestricted OSE management according to investigator discretion. In this case, depatuxizumab mafodotin dose interruption and/or reduction may be used, and any available prophylactic (including addition of ES and VC regimens if not used initially) or supportive care measures may be employed without restriction, at the discretion of the investigator.

Subjects who complete 8 weeks of adjuvant therapy (8 weeks after the first dose of adjuvant depatuxizumab mafodotin) will be allowed to enter the Investigator Discretion phase regardless of CEAE Grade, visual acuity or BCL intervention.

Visual acuity will be measured using the LogMAR scale for visual acuity, while OSE symptom severity will be measured by the Corneal Epithelial AE grading scale (see Section 6.1 and Operations Manual, Section 4.3), which was developed by the sponsor for assessing and managing corneal epitheliopathy associated with ADCs.

[figure not shown]
Effectiveness of the prophylactic strategies will be assessed during the first 8 weeks of each phase of treatment (Chemoradiation Phase and Adjuvant Phase). Subjects who discontinue depatuxizumab mafodotin for any reason will receive regular follow-up for assessment of AEs and ophthalmologic examinations until resolution of OSEs to evaluate the reversibility of depatuxizumab mafodotin-related OSEs.

Figure 1. Study Design

Abbreviations: GBM = glioblastoma; RT = radiation therapy; TMZ = temozolomide

Figure 2. Depatuxizumab Mafodotin Intervention Strategy for Inadequate Control of Ocular Side Effects

4.2 Discussion of Study Design

Suitability of Subject Population

The study population of newly diagnosed GBM with amplified EGFR was selected because depatuxizumab mafodotin is currently being investigated in a late phase clinical trial with this subject population. Ocular side effects are noted to occur at a > 80% frequency in GBM patients with doses currently utilized in the ongoing Phase 2b/3 clinical trial.

Choice of Frontline GBM Therapy

Concomitant RT/TMZ therapy followed by adjuvant TMZ therapy is the established standard-of-care treatment for newly diagnosed GBM, and the dose regimens for RT and TMZ for the current study are consistent with standard of care. Addition of depatuxizumab mafodotin to this standard treatment regimen was generally well tolerated in a Phase 1 study, with dose-limiting toxicity restricted to OSEs, and efficacy is being evaluated in a large Phase 2b/3 study in EGFR-amplified, newly diagnosed GBM.

Choice of Prophylactic Regimens and BCL Intervention

Prophylactic steroid eye drops were instituted early on during the first Phase 1 study in solid tumors to support continued dose escalation. In the ongoing Phase 2b/3 clinical trial in newly diagnosed subjects, all subjects receive prophylactic steroid eye drops with each dose of depatuxizumab mafodotin for 7 consecutive days, starting from 2 days prior to infusion and continuing until 4 days after infusion, making it the standard of care in the depatuxizumab mafodotin clinical development program.

Though not well understood, ocular steroids may slow down the turn-over of transient amplifying cells in the eye and thereby protect them from damage caused by the MMAF toxin portion of depatuxizumab mafodotin that targets cells in rapid division. Although early use has shown that steroid eye drops may reduce the severity of symptoms related to microcyst formation, they generally do not prevent them completely. Because steroid eye drops are used to protect transient amplifying cells during exposure to MMAF, the best time to administer the drops is around the time of infusion when the levels of MMAF are at their peak.

Enhanced steroid treatment regimen will consist of the same steroid eye drops, as those used in the standard steroid arm, administered with the maximal frequency that can be achieved with reasonable expectation of patient compliance. Steroid ointment will be instilled at night, when the patient cannot be expected to self-administer eye drops. This regimen will maximize the exposure of the corneal epithelium to the steroids, allowing examination of the dose-effect relationship. Safety of enhanced steroid treatment will be insured by frequent (every 2 – 4 weeks) targeted ophthalmologic examinations.

The dose of vasoconstrictor was selected based on the maximum dose and duration of treatment recommended for naphazoline hydrochloride 0.012% solution.⁴

The use of therapeutic BCLs can have a major impact on improving eye symptoms, including photophobia, blurred vision and various forms of eye discomfort, and thus minimize the need for depatuxizumab mafodotin dose interruptions and dose reductions.

Appropriateness of Measurements

The LogMAR scale will be the instrument utilized for measuring visual acuity because it is a well-accepted validated tool used in ophthalmology clinical trials designed to evaluate change in visual acuity.⁵

The CEAE grading scale will be used to measure OSE symptom severity. This measure was developed by AbbVie, based on experience with ADC-related microcystic keratopathy caused by depatuxizumab mafodotin, to address inadequacies of the National Cancer Institute Common Terminology Criteria for Adverse Events (NCI CTCAE) system for appropriately capturing symptoms, grading, and making dose modifications for ADC-related corneal toxicity.

5 STUDY ACTIVITIES

5.1 Eligibility Criteria

Subjects must meet all of the following criteria in order to be included in the study. Anything other than a positive response to the questions below will result in exclusion from study participation.

Consent

- ✓ 1. Subjects must voluntarily **sign and date an informed consent**, approved by an Independent Ethics Committee (IEC)/Institutional Review Board (IRB), prior to the initiation of any screening or study-specific procedures.

Demographic and Laboratory Assessments

- ✓ 2. Adult **male or female**, at least 18 years old.
- ✓ 3. **Laboratory values** meeting the following criteria confirming adequate bone marrow, renal, and hepatic function:
 - Bone marrow
 - Absolute neutrophil count $\geq 1,500$ cells/mm³
 - Platelets $\geq 100,000$ cells/mm³
 - Hemoglobin (Hgb) ≥ 9.0 g/dL (transfusion or other intervention to achieve Hgb ≥ 9.0 g/dL is acceptable).
 - Renal function
 - Calculated creatinine clearance ≥ 30 mL/min by the Cockcroft-Gault formula
 - Hepatic function:
 - Total bilirubin $\leq 1.5 \times$ upper limit of normal (ULN). Subjects with Gilbert's syndrome documented in medical history may be enrolled if total bilirubin is $< 3 \times$ ULN.
 - AST $\leq 3 \times$ ULN
 - ALT $\leq 3 \times$ ULN
 - Prothrombin time (PT)/international normalized ratio (INR) ≤ 1.5 . Subjects on anticoagulant (such as coumadin) will have a target PT and INR as determined by the Investigator.
- ✓ 4. Willing or able to comply with procedures required in this protocol.

Disease Activity

- ✓ 5. Diagnosis of newly diagnosed GBM, histologically proven, World Health Organization (WHO) Grade IV GBM or WHO Grade IV gliosarcoma
- ✓ 6. Tumor must demonstrate EGFR amplification by central laboratory

- ✔ 7. Tumor must be supratentorial in location
- ✔ 8. Karnofsky performance status of ≥ 70

Subject History

- ✔ 9. Electrocardiogram without evidence of acute cardiac ischemia ≤ 21 days prior to randomization.
- ✔ 10. Life expectancy of ≥ 3 months.
- ✔ 11. No history of hypersensitivity to any component of TMZ or dacarbazine (DTIC).
- ✔ 12. No history of prior chemotherapy or radiotherapy for cancer of the head and neck region.
- ✔ 13. No history of prior treatment with Gliadel wafers or any other intratumoral or intracavitary treatment.
- ✔ 14. No prior anti-cancer therapy (including chemotherapy, immunotherapy, radiotherapy, hormonal therapy, biologic therapy, or any investigational therapy) prior to 5 years of Study Day 1.
- ✔ 15. No history of a major immunologic reaction to any Immunoglobulin (IgG) containing agent.
- ✔ 16. No clinically significant uncontrolled condition(s) including but not limited to the following:
 - Active uncontrolled infection
 - Symptomatic congestive heart failure
 - Unstable angina pectoris or cardiac arrhythmia
 - Psychiatric illness/social situation that would limit compliance with the study
- ✔ 17. No medical condition which in the opinion of the Investigator places the subject at an unacceptably high risk for toxicities.
- ✔ 18. No other active malignancy within the past 3 years except for any cancer considered cured or non-melanoma carcinoma of the skin.
- ✔ 19. No history of herpetic keratitis.
- ✔ 20. No LASIK (laser-assisted in situ keratomileusis) procedure within the last 1 year or cataract surgery within the last 3 months.
- ✔ 21. No visual condition that compromises the ability to accurately measure visual acuity or assess visual ADLs (e.g., central tumor affecting visual pathways).
- ✔ 22. No infection with hepatitis B virus (i.e., hepatitis B surface antigen) or hepatitis C virus (i.e., positive for hepatitis C antibody). Subjects who have a history of hepatitis C who have documented cures after anti-viral therapy may be enrolled. Subjects with confirmed positive test result for human immunodeficiency virus (HIV), with CD4 count < 200 cells/microliter are excluded.
 - Note that subjects who are HIV positive are eligible, provided they are under treatment with highly active antiretroviral therapy (HAART) and have a CD4 count ≥ 200 cells/microliter within 30 days prior to registration, as the treatments involved in this protocol may be significantly immunosuppressive.

- Note HIV testing is not required for eligibility for this protocol unless mandated by local regulatory authority or ethics committee/institutional review board.

Contraception

- ✓ 23. For all females of childbearing potential, a **negative serum pregnancy test** at the screening visit and a negative urine pregnancy test at baseline prior to the first dose of study drug and monthly throughout the study.
- ✓ 24. Female subjects of childbearing potential must practice at least 1 protocol-specified **method of birth control**, as specified in Section 5.2, that is effective from Study Day 1 through at least 6 months after the last dose of depatuxizumab mafodotin. Female subjects of non-childbearing potential do not need to use birth control.
- ✓ 25. Female who is not **pregnant, breastfeeding, or considering becoming pregnant** during the study or for at least 6 months after the last dose of depatuxizumab mafodotin.
- ✓ 26. **If male**, and subject is **sexually active with female partner(s) of childbearing potential**, he must agree, from Study Day 1 through the entire duration of the study and for at least 6 months after the last dose of depatuxizumab mafodotin, to practice the contraception specified in Section 5.2.
- ✓ 27. Male who is not considering **fathering a child or donating sperm** during the study or for at least 6 months after the last dose of depatuxizumab mafodotin.

Concomitant Medications

- ✓ 28. Suitable for receiving ocular steroids and has none of the following:
 - Any active viral disease of the cornea or conjunctiva, including epithelial herpes simplex keratitis (dendritic keratitis), vaccinia, or varicella; mycobacterial infection of the eye; fungal diseases of ocular structures; or any other contraindication for ocular steroid use.
 - A known or suspected hypersensitivity to any ocular steroid.
 - Primary open angle glaucoma or a history of steroid-induced intraocular pressure elevation.
- ✓ 29. Subject must not anticipate the use of prohibited medications or foods during study participation (see Section 5.3 for additional prohibited medications or foods).

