APPENDIX E. SUBJECTS CONTINUING PARTICIPATION

This appendix outlines the modifications to the study procedures and depatuxizumab mafodotin dosing in subjects who are currently receiving depatuxizumab mafodotin and who choose to continue depatuxizumab mafodotin treatment after the results from the pre-planned interim efficacy analysis for Study M13-813 (INTELLANCE-1).

As a result of the interim efficacy analysis for INTELLANCE-1 study, AbbVie determined it was appropriate to allow subjects who are receiving depatuxizumab mafodotin to continue doing so based on investigator and subject decision.

Subjects who decide to continue treatment with depatuxizumab mafodotin must voluntarily sign and date the updated informed consent form, approved by an Independent Ethics Committee (IEC)/Institutional Review Board (IRB).

Study Activities

Only study activities necessary for study drug dosing, safety monitoring and adverse event reporting will be continued. The revised schedule of study assessments for these subjects is provided in the table below.

Study Activities	28-Day Cycles ^a					Final Study Drug Visit ^d /At Progression	35-Day F/U ^e	49-Day F/U
	Day 1 of Every Cycle (1, 2, 3 etc.)	Day 1 of Odd-Numbered Cycles (1, 3, 5, etc.)	Day 1 of Cycle 2	Day 15 of Every Cycle ^b	Day 22 of Every Cycle ^c			
Symptom-directed Physical Exam	X ^f			X ^f				
Ophthalmology Exams		X ^g				X ^g	X ^g	
Chemistry	X					X	X	
Hematology	X				X	X	X	
Adverse Event Assessment and Concomitant Medications	X			X		X	X	X ^k
Temozolomide Administration	X ^h							
Depatuzumab Mafodotin Administration	X ⁱ			X ⁱ				
Treatments for OSE	X ⁱ			X ⁱ				

F/U = Follow-up; OSE = ocular side effect

- Assessments will be based on 28-day treatment cycles, with the first cycle starting approximately 4 weeks after completion of radiation therapy. Subjects will receive concomitant TMZ and depatuzumab mafodotin for the first 6 cycles, and study drug monotherapy for an additional 6 cycles or until disease progression or study drug discontinuation.
- Day 15 visit will not be performed after discontinuation of depatuzumab mafodotin treatment.

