- As per TMZ prescribing information, during the 28-day cycle of TMZ, a blood count for ANC and platelets should be performed 21 days (\pm 2 days) after the start of each TMZ cycle. If the ANC falls below 1,500/ μ L or if the platelet count falls below 100,000/ mm^3 , then blood counts should be performed weekly until recovery to these levels before TMZ dosing. A certified local lab may be used instead of central lab; if so, ANC and platelet results should be reported in the eCRF. Day 22 testing may be omitted for cycles in which TMZ is not administered or if local prescribing information allows for a different testing schedule for ANC and platelets.
- Final Study Drug Visit to be performed approximately 14 days after last dose of depatuzumab mafodotin.
- To be performed 35 days (\pm 3 days) after the last dose of depatuzumab mafodotin. If the Final Study Drug Visit is more than 35 days after the last dose of study drug, then 35-day safety follow-up procedures will not be performed.
- Physical exams will be performed only as needed for safety management and AE/SAE reporting.
- Ophthalmology exams will be performed only as needed for safety management and AE/SAE reporting. The last ophthalmology exam following discontinuation of depatuzumab mafodotin may be done at the 35-Day F/U or 49-Day F/U Visit. Targeted ophthalmology exam data will not be collected by the Sponsor.
- TMZ will be administered once daily on Days 1 through 5 of each 28-day cycle for 6 cycles per the local prescribing information.

- i. Depatuxizumab mafodotin infusion will be administered on Day 1 and Day 15 of each 28-day cycle for 12 cycles.
- j. Patient will receive management of ocular side effects as per investigator discretion. In this case, depatuxizumab mafodotin dose interruption and/or reduction may be used, and any available prophylactic or supportive care measures may be employed without restriction, at the discretion of the investigator. Refer to Section 5.7 of the protocol.
- k. If the subject is unable to return to the site for the Day 49 Follow-Up Visit, a phone call may be conducted to obtain AE/SAE and concomitant medication information.

Depatuxizumab Mafodotin Administration and Individual Subject Discontinuation

Depatuxizumab mafodotin will be administered as described in the protocol.

Subjects may continue receiving depatuxizumab mafodotin while drug supply is available, as long as disease progression has not been determined.

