Depatuxizumab Mafodotin Toxicity Management and Individual Subject Dose Modifications

Section 6.3 of the protocol provides guidance for toxicity management and dose modifications.

Adverse Events and Concomitant Medications

Adverse event and concomitant medications data will be collected to support regulatory safety reporting requirements.

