3.4 Eligibility Criteria

Eligibility Criteria will be assessed at Screening, see Protocol Section 5.1.

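### Appendix E, the schedule for subjects still receiving depatuxizumab mafodotin, omits the monthly pregnancy test that criterion 23 requires of females of childbearing potential

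*Protocol*

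**What the plan says.** Criterion 23 in Protocol 5.1 covers females of childbearing potential. After a serum test at screening it asks for "a negative urine pregnancy test at baseline prior to the first dose of study drug and monthly throughout the study". It stands in the current protocol (version 4.0). Three places put it into a schedule: the activity table in Protocol Appendix D (monthly, urine), the Adjuvant Phase visit lists in Operations Manual 2.1 (monthly, or as local rules require), and the 35- and 49-day follow-up lists in Operations Manual 2.2.

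For subjects who stay on drug after the INTELLANCE-1 interim result, Protocol 2.2 says that procedures are changed as Appendix E describes. Appendix E states: "Only study activities necessary for study drug dosing, safety monitoring and adverse event reporting will be continued". It then says: "The revised schedule of study assessments for these subjects is provided in the table below". Dosing goes on: "Depatuxizumab mafodotin infusion will be administered on Day 1 and Day 15 of each 28-day cycle for 12 cycles". Temozolomide is given alongside it early on: "Subjects will receive concomitant TMZ and depatuzumab mafodotin for the first 6 cycles".

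The Pregnancy paragraph of Protocol 6.1 requires depatuxizumab mafodotin to stop at once if a test is positive or the subject reports a pregnancy. Section 5.5 requires withdrawal of a subject who becomes pregnant on study drug.

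**The concern.** A standing rule asks for a monthly test, and the schedule that sites now follow does not list it. Appendix E is worded restrictively and supplies its own table, so a site working from it as written would have no prompt to test. Pregnancy would then be picked up mainly by self-report, or by testing that a site does on its own initiative. Meanwhile an antibody-drug conjugate carrying a microtubule-disrupting toxin, and temozolomide in the first 6 cycles, would still be given. Of the two triggers for the Section 6.1 stop rule, the one that does not depend on the subject noticing and reporting would no longer be scheduled. What is at stake is subject safety, not the analysis.

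**Working it through.** No published figure needs reproducing. The check is a comparison of texts, followed by a simple count.

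**Rule against schedule**

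| Place | Urine pregnancy test after the first dose |
|---|---|
| Protocol 5.1, criterion 23 | Monthly throughout the study |
| Protocol Appendix D | Monthly, and at follow-up |
| Operations Manual 2.1, Adjuvant Phase | Monthly, or per local rules |
| Operations Manual 2.2, 35- and 49-day visits | Listed at each |
| Protocol Appendix E, table and footnotes a to k | None |

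The Appendix E table has eight rows: physical exam, ophthalmology, chemistry, hematology, adverse events with concomitant medications, temozolomide, depatuxizumab mafodotin, and treatments for ocular side effects. The rows and footnotes are readable, so the absence does not look like a loss in PDF extraction.

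**Does anything in Appendix E bring the test back?** It refers to the body of the protocol in three ways.
- One footnote points to Section 5.7 for ocular management. Section 5.7 contains no pregnancy test.
- The toxicity paragraph says: "Section 6.3 of the protocol provides guidance for toxicity management and dose modifications". Section 6.3 contains no pregnancy test either.
- A general sentence says the drug is administered as the protocol describes. That concerns administration and schedules no test.

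None of these reaches criterion 23 or the Pregnancy paragraph of Section 6.1. The Operations Manual adds: "Eligibility Criteria will be assessed at Screening, see Protocol Section 5.1". So for a subject long past screening, the visit schedule is what prompts the test.

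**Count while dosing.** Let m be the number of 28-day cycles still to be given under Appendix E, and assume one test per cycle.
- Infusions = 2m (Day 1 and Day 15).
- Tests required by criterion 23 = m; tests scheduled = 0.
- m = 1: 2 infusions, 1 test. m = 6: 12 and 6. m = 12 (the 12-cycle limit): 24 and 12.

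**After the last dose.** The 35- and 49-day visits account for up to 2 further tests. They cannot prevent an infusion, and those visits' procedures can be waived when the final visit is late (Appendix E footnote e for Day 35; the note in Operations Manual 2.2 for Day 49).

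**Gap after the last Day 1 test, if the row is restored.**
- Last dose on Day 1: 35 days to the 35-day visit.
- Last dose on Day 15: 14 + 35 = 49 days.
- With a test at the Final Study Drug Visit (about 14 days after the last dose), the second case splits into 14 + 14 = 28 days and 35 - 14 = 21 days.

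The main schedules are not clear on that visit. The Appendix D pregnancy row, as extracted, appears to carry a tick there, while the Operations Manual list for the visit has no test. The copy of the table in the SAP appendix does not settle it, and the table layout is damaged.

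**The case against.** The strongest reply is that Appendix E is silent rather than contradictory. It keeps whatever dosing and safety monitoring need, and a test whose positive result stops the drug can fairly be counted among those needs. If criterion 23 is live it already binds sites; if it is only a screening criterion, there is nothing to conflict with.

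Part of this stands. Appendix E does not waive the test, and a careful site could keep testing under criterion 23 or local rules. But criterion 23, by its own wording, sets a frequency for the whole study, so it is not a screening check alone. And the table is how Appendix E says which monitoring continues: it spells out even the Day 22 blood counts. A rule that is in force but missing from the operative schedule is a disagreement that the sponsor should remove.

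Several further points limit the matter. Contraception stays mandatory (criterion 24, Section 5.2), which lowers the risk without replacing the test. Enrollment closed at 40 subjects. The updated consent form is not available for review. The Operations Manual allows local frequency and does not demand a pre-dose test on Day 1.

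A reader might infer that the amendment withdrew pregnancy testing, or that women were in fact dosed untested. The documents support neither: criterion 23 was left in place, and nothing shows what sites did.

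**Conclusion.** The point holds as an inconsistency that bears on subject safety. For females of childbearing potential, criterion 23 requires a monthly urine test and Appendix E schedules none, so the Section 6.1 stop rule loses its scheduled trigger while dosing continues.

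The size is 1 unscheduled test for every 2 infusions, up to 12 tests and 24 infusions for a woman whose whole 12-cycle adjuvant phase falls under Appendix E, and fewer for anyone who had already completed cycles. Up to 2 follow-up tests are also missing. These counts assume one test per 28-day cycle; the finding itself does not depend on them. The number of such women among the 40 enrolled is not given and could be 0. No endpoint, estimate or analysis is affected.

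It would go too far to say that every continuing subject is affected, or that each missing test corresponds to a preventable exposure. The rule covers only females of childbearing potential, and the follow-up tests come after the last dose.

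**What to change.** Add one row to the Appendix E table: urine pregnancy test, females of childbearing potential, with a reference to criterion 23. Schedule it at least monthly while depatuxizumab mafodotin or temozolomide is given, and at the 35- and 49-day visits. Before dosing on Day 1 of each 28-day cycle is the convenient time, or more often where local rules require. That timing is a suggestion; neither criterion 23 nor the Operations Manual fixes it.

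Add a footnote for Day 49, because Appendix E allows that contact to be remote: "If the subject is unable to return to the site for the Day 49 Follow-Up Visit, a phone call may be conducted". In that case the test is done locally.

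Reconcile the Final Study Drug Visit between Appendix D and Operations Manual 2.1, and preferably include a test there, which closes the gap of up to 49 days after a Day 15 last dose.

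The cost is one row and one footnote, by a short amendment or administrative letter. Apart from a Day 49 contact by phone, every test falls at a visit that Appendix E already schedules, and only females of childbearing potential are tested. If no such woman is continuing, the change costs nothing in practice.
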